### **7.3.3 Immediate Reporting of Adverse Events to Incyte and Merck**

#### **7.3.3.1 Serious Adverse Events**

A serious adverse event is any adverse event occurring at any dose or during any use of Merck/Incyte products that:

- Results in death;
- Is life threatening;
- Results in persistent or significant disability/incapacity;
- Results in or prolongs an existing inpatient hospitalization;
- Is a congenital anomaly/birth defect;
- Is a new cancer (that is not a condition of the study);

Protocol #: UC IRB17-1539

Version Date: 1/23/2018

- Is associated with an overdose;
- Is an other important medical event

Refer to Table 8 for additional details regarding each of the above criteria.

Any serious adverse event, or follow up to a serious adverse event, including death due to any cause other than progression of the cancer under study that occurs to any subject from the time of first dose of study drug through 90 days following cessation of treatment, or the initiation of new anti-cancer therapy, whichever is earlier, whether or not related to Merck/Incyte products, must be reported within 24 hours to the Sponsor and within 2 working days to Incyte/Merck Global Safety as described in section 10.7.

Non-serious Events of Clinical Interest will be forwarded to Incyte / Merck Global Safety and will be handled in the same manner as SAEs.

Additionally, any serious adverse event, considered by an investigator who is a qualified physician to be related to Merck/Incyte products that is brought to the attention of the investigator at any time outside of the time period specified in the previous paragraph also must be reported immediately to the Sponsor and to Merck /Incyte as described in section 10.7.

This study will be conducted under an IND held by [name] at the University of Chicago. Annual Progress Reports will be submitted as required by FDA. Additionally the IND holder will submit a copy of these reports to Incyte/Merck & Co., Inc. (Attn: Worldwide Product Safety; [contact]) at the time of submission to FDA.

All subjects with serious adverse events must be followed up for outcome.

The investigator must assess and record the relationship of each SAE to the specific study drug, and report this as described in section 10.7. The original copy of the SAE Report and the fax confirmation sheet must be kept at the study site.

Follow-up information is sent to the same person to whom the original SAE Report Form was sent, using a new SAE Report Form stating that this is a follow-up to the previously reported SAE and giving the date of the original report. Each re-occurrence, complication, or progression of the original event should be reported as a follow-up to that event regardless of when it occurs. The follow-up information should describe whether the event has resolved or continues, if and how it was treated, whether the blind was broken or not (if applicable), and whether the patient continued or withdrew from study participation.

### **7.3.3.2 Events of Clinical Interest**

Selected non-serious and serious adverse events are also known as Events of Clinical Interest

(ECI) and must be reported within 24 hours to the PI as well as Incyte/Merck.

Protocol #: UC IRB17-1539

Version Date: 1/23/2018

For the time period beginning when the consent form is signed until treatment allocation/randomization, any ECI, or follow up to an ECI, that occurs to any subject must be reported within 24 hours if it causes the subject to be excluded from the trial, or is the result of a protocol-specified intervention, including but not limited to washout or discontinuation of usual therapy, diet, placebo treatment or a procedure.

For the time period beginning at treatment allocation through 30 days following cessation of treatment, any ECI, or follow up to an ECI, whether or not related to study products, must be reported within 24 hours.

Events of clinical interest for this trial include:

1. an overdose of one of the investigational products, as defined below under Definition of an Overdose for This Protocol and Reporting of Overdose, that is not associated with clinical symptoms or abnormal laboratory results.
2. an elevated AST or ALT lab value that is greater than or equal to 3X the upper limit of normal and an elevated total bilirubin lab value that is greater than or equal to 2X the upper limit of normal and, at the same time, an alkaline phosphatase lab value that is less than 2X the upper limit of normal, as determined by way of protocol-specified laboratory testing or unscheduled laboratory testing.\*

\*Note: These criteria are based upon available regulatory guidance documents. The purpose of the criteria is to specify a threshold of abnormal hepatic tests that may require an additional evaluation for an underlying etiology.

### **7.3.4 Evaluating Adverse Events**

An investigator who is a qualified physician will evaluate all adverse events according to the NCI Common Terminology for Adverse Events (CTCAE), version 4.0. Any adverse event which changes CTCAE grade over the course of a given episode will have each change of grade recorded on the adverse event case report forms/worksheets.

All adverse events regardless of CTCAE grade must also be evaluated for seriousness.

### **7.3.5 Definition of an Overdose for This Protocol and Reporting of Overdose**

In this trial, an overdose is any dose higher than  $\geq 1000$  mg (5 times the dose) of pembrolizumab or  $\geq 1000$  mg of epacadostat. No specific information is available on the treatment of overdose of pembrolizumab or epacadostat. In the event of overdose, the subject should be observed closely for signs of toxicity. Appropriate supportive treatment should be provided if clinically indicated.

If an adverse event(s) is associated with (“results from”) the overdose, the adverse event(s) is reported as a serious adverse event, even if no other seriousness criteria are met.

Protocol #: UC IRB17-1539

Version Date: 1/23/2018

If a dose meeting the protocol definition of overdose is taken without any associated clinical symptoms or abnormal laboratory results, the overdose is reported as a non-serious Event of Clinical Interest (ECI), using the terminology “accidental or intentional overdose without adverse effect.”

All reports of overdose with and without an adverse event must be reported by the investigator within 24 hours to Incyte/Merck.

Protocol #: UC IRB17-1539

Version Date: 1/23/2018

**Table 8 Evaluating Adverse Events**

An investigator who is a qualified physician, will evaluate all adverse events as to:

V4.0 CTCAE Grading	Grade 1	Mild; asymptomatic or mild symptoms; clinical or diagnostic observations only; intervention not indicated.
	Grade 2	Moderate; minimal, local or noninvasive intervention indicated; limiting age-appropriate instrumental ADL.
	Grade 3	Severe or medically significant but not immediately life-threatening; hospitalization or prolongation of hospitalization indicated; disabling; limiting self-care ADL.
	Grade 4	Life threatening consequences; urgent intervention indicated.
	Grade 5	Death related to AE
Seriousness	A serious adverse event is any adverse event occurring at any dose or during any use of Merck/Incyte product that:	
	†Results in death; or	
	†Is life threatening; or places the subject, in the view of the investigator, at immediate risk of death from the event as it occurred (Note: This does not include an adverse event that, had it occurred in a more severe form, might have caused death.); or	
	†Results in a persistent or significant disability/incapacity (substantial disruption of one's ability to conduct normal life functions); or	
	†Results in or prolongs an existing inpatient hospitalization (hospitalization is defined as an inpatient admission, regardless of length of stay, even if the hospitalization is a precautionary measure for continued observation. (Note: Hospitalization [including hospitalization for an elective procedure] for a preexisting condition which has not worsened does not constitute a serious adverse event.); or	
	†Is a congenital anomaly/birth defect (in offspring of subject taking the product regardless of time to diagnosis); or	
	Is a new cancer; (that is not a condition of the study) or	
	Is an overdose (whether accidental or intentional). Any adverse event associated with an overdose is considered a serious adverse event. An overdose that is not associated with an adverse event is considered a non-serious event of clinical interest and must be reported within 24 hours.	
	Other important medical events that may not result in death, not be life threatening, or not require hospitalization may be considered a serious adverse event when, based upon appropriate medical judgment, the event may jeopardize the subject and may require medical or surgical intervention to prevent one of the outcomes listed previously (designated above by a †).	
Duration	Record the start and stop dates of the adverse event. If less than 1 day, indicate the appropriate length of time and units	
Action taken	Did the adverse event cause the Merck/Incyte product to be discontinued?	
Relationship to test drug	Did the Merck / Incyte product cause the adverse event? The determination of the likelihood that the Merck /Incyte product caused the adverse event will be provided by an investigator who is a qualified physician. The investigator's signed/dated initials on the source document or worksheet that supports the causality noted on the AE form, ensures that a medically qualified assessment of causality was done. This initialed document must be retained for the required regulatory time frame. The criteria below are intended as reference guidelines to assist the investigator in assessing the likelihood of a relationship between the test drug and the adverse event based upon the available information. The following components are to be used to assess the relationship between the Merck/Incyte product and the AE; the greater the correlation with the components and their respective elements (in number and/or intensity), the more likely the Merck /Incyte product caused the adverse event (AE):	
	Exposure	Is there evidence that the subject was actually exposed to the Merck/Incyte products such as: reliable history, acceptable compliance assessment (pill count, diary, etc.), expected pharmacologic effect, or measurement of drug/metabolite in bodily specimen?

Protocol #: UC IRB17-1539

Version Date: 1/23/2018

Time Course	Did the AE follow in a reasonable temporal sequence from administration of the Merck/Incyte products? Is the time of onset of the AE compatible with a drug-induced effect (applies to trials with investigational medicinal product)?
Likely Cause	Is the AE not reasonably explained by another etiology such as underlying disease, other drug(s)/vaccine(s), or other host or environmental factors

Relationship to investigational product (continued)	The following components are to be used to assess the relationship between the test drug and the AE: (continued)	
	Dechallenge	Was the Merck/Incyte products discontinued or dose/exposure/frequency reduced? If yes, did the AE resolve or improve? If yes, this is a positive dechallenge. If no, this is a negative dechallenge. (Note: This criterion is not applicable if: (1) the AE resulted in death or permanent disability; (2) the AE resolved/improved despite continuation of the Merck/Incyte products; or (3) the trial is a single-dose drug trial); or (4) Merck/Incyte products(s) is/are only used one time.)
	Rechallenge	Was the subject re-exposed to the Merck/Incyte products in this study? If yes, did the AE recur or worsen? If yes, this is a positive rechallenge. If no, this is a negative rechallenge. (Note: This criterion is not applicable if: (1) the initial AE resulted in death or permanent disability, or (2) the trial is a single-dose drug trial); or (3) Merck/Incyte products(s) is/are used only one time). NOTE: IF A RECHALLENGE IS PLANNED FOR AN ADVERSE EVENT WHICH WAS SERIOUS AND WHICH MAY HAVE BEEN CAUSED BY THE STUDY DRUG, APPROVAL FROM THE PI IS REQUIRED
	Consistency with Trial Treatment Profile	Is the clinical/pathological presentation of the AE consistent with previous knowledge regarding the Merck/Incyte products or drug class pharmacology or toxicology?
The assessment of relationship will be reported on the case report forms /worksheets by an investigator who is a qualified physician according to his/her best clinical judgment, including consideration of the above elements.		
Record one of the following	Use the following scale of criteria as guidance (not all criteria must be present to be indicative of a Merck/Incyte products relationship).	
Yes, there is a reasonable possibility of Merck/Incyte products relationship.	There is evidence of exposure to the Merck/Incyte products. The temporal sequence of the AE onset relative to the administration of the Merck/Incyte products is reasonable. The AE is more likely explained by the Merck/Incyte products than by another cause.	
No, there is not a reasonable possibility Merck/Incyte products relationship	Subject did not receive the Merck/Incyte products OR temporal sequence of the AE onset relative to administration of the Merck/Incyte products is not reasonable OR there is another obvious cause of the AE. (Also entered for a subject with overdose without an associated AE.)	

Protocol #: UC IRB17-1539  
Version Date: 1/23/2018

### **7.3.6 Sponsor Responsibility for Reporting Adverse Events**

All Adverse Events will be reported to regulatory authorities, IRB/IECs and investigators in accordance with all applicable laws and regulations.

### **7.4 Efficacy assessment**

The primary study endpoint is **Response Rate** assessed per RECIST 1.1.

Disease progression (PD) will be evaluated by clinical and radiographic methods and date of progression will be recorded. Radiographic progression should be confirmed with a second scan 4-8 weeks after initial scan and treatment can continue until then.

If in question, disease progression should be confirmed pathologically. Site of disease progression will be classified as local (progression at primary tumor site), regional (progression in cervical lymph nodes), and/or distant (metastatic disease).

A diagnosis of second primary tumor must be confirmed pathologically. Deaths on study should be classified as disease (HNSCC), non-disease, or study treatment related.

Protocol #: UC IRB17-1539  
Version Date: 1/23/2018

## 8.0 STATISTICAL ANALYSIS PLAN

### 8.1 Statistical Analysis Plan

**This study includes two cohorts. These will be handled as parallel cohorts/trials with the same statistical assumptions for both cohorts:**

#### **Primary Outcome: Response rate**

Clinical and pathologic response rates will be determined and 90% confidence intervals obtained using the exact binomial distribution.

A Simon's two-stage design (Simon, 1989) will be used – using the Minimax variant - for both cohorts. The null hypothesis that the true response rate is 3% [ $p_0$ ] (*assuming poor efficacy of e.g. pembrolizumab treatment in patients, who have failed prior PD-1/PD-L1 therapy*) will be tested against a one-sided alternative. In the first stage, 10 [ $n_1$ ] patients will be accrued. If there are no responses [ $r_1$ ] in these 10 [ $n_1$ ] patients, the study will be stopped.

Otherwise, 5 additional patients will be accrued for a total of 15 [ $n$ ] patients. The null hypothesis will be rejected if 2 or more responses are observed in 15 patients. This design yields a type I error rate of 0.0667 and 80% power when the true response rate is 20%.

A response rate of 20% would be considered clinically meaningful for HNC in the absence of alternative treatment options in the 2nd/3rd line setting (after PD-1/PD-L1 failure) and further development of pembrolizumab + epacadostat would proceed.

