#### Hypotheses:

**Cohort 1:** In patient with prior response to anti-PD-1/PD-L1+ therapy and subsequent (acquired) resistance combined IDO1 and PD-1 inhibition will re-induce responses.

**Cohort 2:** In patients with suboptimal benefit from prior anti-PD-1/PD-L1 therapy combined IDO1 and PD-1 inhibition will induce clinically meaningful responses.

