### 3.3 Exploratory/Translational Objectives

- (1) Interferon-gamma Gene Expression Profile (GEP) (*Seiwert ASCO 2015, Ribas ASCO 2015*) and evaluation of RR, PFS, and OS in GEP positive and GEP negative patients.
- (2) Determine the micro-environment that underlies resistance/suboptimal treatment
  - a) underlying degree of tumor inflammation
  - b) Baseline PD-L1 expression
  - d) Determine underlying Interferon Gamma signature
- (3) Assess underlying mutational burden (*Snyder 2014*)

**Preclinical hypothesis:** IDO1 inhibition will alter the micro-environment to a be “more T-cell inflamed” and make tumors amenable to benefit from anti-PD-1 treatment (when given concurrently with IDO1 inhibition). Hence we will evaluate tumors, with prior response exhibiting acquired resistance as well as tumors with minor/suboptimal benefit from prior PD-1/PD-L1 therapy for evidence (at baseline) of suboptimal immune microenvironmental conditions.

Protocol #: UC IRB17-1539

Version Date: 04/24/2019

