## **5.0 METHODOLOGY**

### **5.1 Entry Criteria / Eligibility**

#### **5.1.1 Diagnosis/Condition for Entry into the Trial**

#### **5.1.2 Subject Inclusion Criteria**

In order to be eligible for participation in this trial, the subject must fulfill the following entry criteria:

1. Patients must have histologically confirmed squamous cell carcinoma of the head and neck (unresectable and not amenable to curative intent therapy)
2. Meet criteria for either the Acquired Resistance OR the Suboptimal Benefit Cohort
  - a. **Acquired Resistance is defined as (i and ii must both be met):**
    - i. **Prior *benefit* from anti-PD-1/PD-L1 therapy defined as a) prior response, *and/or* b)  $\geq 5$  months of stable disease (SD). Intervening therapies are allowed.**
    - ii. **Progressive Disease (PD) on recent scans**
  - b. **Suboptimal Benefit is defined as (i and ii must both be met):**
    - i. **Prolonged stable disease  $\geq 5$  months OR Suboptimal response ( $>10\%$  &  $<50\%$  shrinkage per RECIST at any evaluation timepoint)**
    - ii. **Ongoing stable disease on recent scans**
    - iii. **Last treatment with an anti-PD-1/PD-L1 agent within 6 weeks prior to starting protocol treatment**
3. Archival tissue for PD-L1 staining (alternatively a new biopsy (core) at baseline can be used). A minimum of 10 slides is required (unless approval from the PI is obtained)
4. Measurable disease per RECIST 1.1.
5. Known HPV status
6. ECOG performance status 0 or 1
7. Be willing and able to provide written informed consent/assent for the trial.
8. Be  $\geq 18$  years of age on day of signing informed consent.
9. Demonstrate reasonable organ function as defined in
10. Table 1, all screening labs should be performed within 10 days of treatment initiation.

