### 5.1.3 Subject Exclusion Criteria

The subject must be excluded from participating in the trial if the subject:

1. Is currently participating and receiving study therapy or has participated in a study of an investigational agent and received study therapy or used an investigational device within 2 weeks of the first dose of treatment.

2. Has a diagnosis of immunodeficiency or is receiving systemic steroid therapy or any other form of immunosuppressive therapy within 7 days prior to the first dose of trial treatment.
3. Has a known history of active TB (Bacillus Tuberculosis)
4. Has hypersensitivity to pembrolizumab, epacadostat or any of its excipients.
5. Has had a prior anti-cancer monoclonal antibody (mAb) within 3 weeks prior to study Day 1, or targeted small molecule therapy within 2 weeks prior to study Day 1, or who has not recovered (i.e.,  $\leq$  Grade 1 or at baseline) from adverse events due to agents administered more than 4 weeks earlier.
6. Has not recovered from prior surgery, chemotherapy or radiation therapy from adverse events due to a previous treatment/ administered agent (i.e.,  $\leq$  Grade 1 or return to baseline prior to treatment).
  - Note: Subjects with  $\leq$  Grade 2 neuropathy, any grade hearing loss or tinnitus, or typical side effects from radiotherapy are an exception to this criterion and may qualify for the study.
  - Note: If subject received major surgery, they must have recovered adequately from the toxicity and/or complications from the intervention prior to starting therapy.
7. Has a known additional malignancy that is progressing or requires active treatment. Exceptions include basal cell carcinoma of the skin or squamous cell carcinoma of the skin that has undergone potentially curative therapy or in situ cervical cancer or any tumors that are not likely to influence live expectancy in the subsequent 3 years without active treatment (e.g. low grade prostate cancer in absence of therapy).
8. Has known active (=growing) central nervous system (CNS) metastases and/or carcinomatous meningitis. Radiation or resected brain metastasis are acceptable if clinically stable.

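### Does the 3% null response rate, explained by failure of earlier PD-1/PD-L1 therapy, undermine the type I error stated for the stable-disease cohort?

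*Combined protocol and SAP*

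**What the plan says.** Section 8.1 introduces the two cohorts with the statement "These will be handled as parallel cohorts/trials with the same statistical assumptions for both cohorts". Each uses a Simon two-stage minimax design. Ten patients enter first, and the cohort stops if none responds. Otherwise five more are added, and 3% is rejected if at least 2 of the 15 respond. The plan gives a type I error of 0.0667 and 80% power at a true rate of 20%. The only reason offered for 3% is the parenthesis "assuming poor efficacy of e.g. pembrolizumab treatment in patients, who have failed prior PD-1/PD-L1 therapy". Response rates are to be reported with exact binomial 90% confidence intervals.

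Section 5.1.2 separates the cohorts by current disease status. Cohort 1 (acquired resistance) needs earlier benefit followed by progression. Cohort 2 (suboptimal benefit) needs either at least 5 months of stable disease or shrinkage between 10% and 50%, together with "Ongoing stable disease on recent scans". A third Cohort 2 item reads "Last treatment with an anti-PD-1/PD-L1 agent within 6 weeks prior to starting protocol treatment". Section 3.1 states the Cohort 2 hypothesis as "In patients with suboptimal benefit from prior anti-PD-1/PD-L1 therapy combined IDO1 and PD-1 inhibition will induce clinically meaningful responses".

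**The concern.** The reason given for 3% describes patients in whom PD-1/PD-L1 therapy has failed. That suits Cohort 1, who enter with progression. Cohort 2 enter while their disease is controlled, and Section 3.3 also names them separately, as "tumors with minor/suboptimal benefit from prior PD-1/PD-L1 therapy". The recency item, read with the exclusion "Has had a prior anti-cancer monoclonal antibody (mAb) within 3 weeks prior to study Day 1" in Section 5.1.3, would put the last antibody dose roughly 3 to 6 weeks before Day 1. For Cohort 2 the trial would then come close to continuing PD-1 blockade and adding epacadostat. The natural benchmark is the response rate on continued blockade alone in stable patients, which the documents never give.

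At stake is how a Cohort 2 success is read. If background responses are somewhat more frequent than 3%, two responses in 15 would occur by chance more often than 0.0667 suggests, and could be taken as an effect of epacadostat.

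**Working it through.** **Inputs (Section 8.1).** n1 = 10, stop at 0 responses; n = 15; reject at 2 or more; null 3%; target 20%.

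**Formula.** Let X1 be the responses among the first 10 patients and X2 those among the next 5. The rule is met if X1 ≥ 2, or if X1 = 1 and X2 ≥ 1. Hence

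P(meet rule | p) = P(X1 ≥ 2) + P(X1 = 1) × [1 − (1 − p)^5].

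**Reproducing the plan's figures.**
- p = 0.03: P(X1 ≥ 2) = 0.0345; P(X1 = 1) = 0.2281; 1 − 0.97^5 = 0.1413. Total 0.0345 + 0.2281 × 0.1413 = 0.0345 + 0.0322 = **0.0667**, as stated.
- p = 0.20: 0.6242 + 0.2684 × 0.6723 = 0.6242 + 0.1805 = **0.8047**, in line with the stated 80%.

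**Sensitivity to the background rate.** The documents give no rate for Cohort 2, so the values other than 3% are assumptions.

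| Assumed background rate | Chance of meeting the rule |
|---|---|
| 2% | 0.032 |
| 3% | 0.067 |
| 4% | 0.109 |
| 5% | 0.157 |

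The probability reaches 0.10 at about 3.8%.

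**What the documents offer as evidence.**
- Section 4.1.7 gives a response rate of 16-18% for PD-1 blockade in head and neck cancer. It is not reported for patients already stable on such therapy.
- Section 4.1.6 describes 10 immunotherapy-pretreated patients given epacadostat with ipilimumab. All disease control was stable disease, so there were 0 responses in 10. The one-sided 95% exact upper limit is 1 − 0.05^(1/10) = 25.9%. The regimen differs, and the result neither supports nor contradicts 3%.

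**What a design change would cost.**
- Requiring 3 or more of 15, with the same first stage, gives error 0.036 at 5%, but power at 20% is 0.596. The loss is 0.805 − 0.596 = 0.209.
- Raising the null to 5% with power of at least 0.80 at 20% needs 21 patients if the error may be up to 0.10 (actual 0.080), or 27 if it must not exceed 0.0667 (actual 0.042). That is 6 or 12 more than the planned 15.

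**What the planned interval shows at the boundary.** For 2 of 15, the lower limit of the ordinary exact 90% interval solves P(X ≥ 2 | n = 15, p) = 0.05, which gives p of about 2.4%. At p = 0.03 the same tail is 0.073, above 0.05. A bare two-response success would therefore be reported with an interval that still includes 3%.

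**The case for a change.** The strongest case for acting is that Section 8.1 treats the cohorts as parallel trials, so each carries its own primary conclusion, and Cohort 2's rests on a benchmark explained for other patients. The protocol's vocabulary lends support: in the Cohort 1 definition, at least 5 months of stable disease counts as earlier benefit, alongside the first limb "from anti-PD-1/PD-L1 therapy defined as a) prior response", and the same duration is one route into Cohort 2. The error is steep in the background rate, passing 0.10 less than one percentage point above the null. A few sentences stating the basis for 3%, tabulating the error over a range and limiting the Cohort 2 claim would cost no patients.

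The mismatch of wording stands, as does the absence of a Cohort 2 background rate. The rest carries less weight:

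- **The vocabulary is not decisive.** Section 4.2.4.1 places the whole trial in a setting of PD-1/PD-L1 treatment failure, and Section 8.1 uses failure again for the 20% target that covers both cohorts. The word serves as a loose umbrella. The definition that counts long stable disease as benefit is Cohort 1's own, so benefit and failure coexist in this protocol.
- **The 3-to-6-week window is uncertain.** It needs the recency item to be binding, while the header of the Cohort 2 definition requires only items i and ii. Ongoing stable disease is required on either reading.
- **The additions would settle nothing.** They would leave the null, sample size and cut-off untouched, and no figure shown to be wrong would be corrected. A sentence saying that rejection shows a rate above 3% would sit badly with the planned interval at 2 of 15. That a single-arm trial cannot isolate epacadostat's contribution is true of any such combination study, and the Cohort 2 hypothesis claims only responses on the combination.

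**Conclusion.** The explanation of 3% fits Cohort 2 loosely, but no change to the plan follows. The figure 0.0667 is the exact size of the stated test of 3%, whoever is enrolled. If Cohort 2's true rate were 5%, rejecting 3% would be a correct rejection; the open question would be whether 3% was a useful benchmark. That question hangs over any single-arm trial with a historical null, and here it applies to Cohort 1 as well, since 3% has no cited source there.

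The size of the uncertainty is 0.032 to 0.157 over assumed background rates of 2% to 5%. It runs in both directions, and nothing in the documents locates Cohort 2 within that range. Guarding against the upper end would cost about 21 points of power or 6 to 12 more patients in Cohort 2, on the strength of a rate nobody has estimated. Keeping the present rule is a fair trade-off for a small phase II study.

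The gap in rationale is one that analysts can fill at reporting: say what supports 3% for stable patients, or that nothing specific does, and read the Cohort 2 result through the planned exact 90% interval. This conclusion assumes that the interval is reported for each cohort, as the parallel handling in Section 8.1 implies.

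### At 2 responses in 15 (13.3%), does Section 8.1 leave open whether the count rule or the 20% response rate decides further development?

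*Combined protocol and SAP*

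**What the plan says.** Section 8.1 (Primary Outcome: Response rate) sets up a Simon two-stage design and applies it separately to both cohorts: "These will be handled as parallel cohorts/trials with the same statistical assumptions for both cohorts". The null value is 3% ("The null hypothesis that the true response rate is 3" percent), with a one-sided alternative. Ten patients enter first, and the cohort stops if none responds. Otherwise five more are added, and "The null hypothesis will be rejected if 2 or more responses are observed in 15 patients". The section states a type I error of 0.0667 and "80% power when the true response rate is 20" percent.

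The next paragraph says "A response rate of 20% would be considered clinically meaningful for HNC", given the lack of other options after failure of PD-1/PD-L1 treatment, and that "further development of pembrolizumab + epacadostat would proceed". The response rate is also to be reported with "90% confidence intervals obtained using the exact binomial distribution". For Cohort 2, the hypothesis in Section 3.1 is that "combined IDO1 and PD-1 inhibition will induce clinically meaningful responses", with no rate attached.

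**The concern.** The rejection rule and the remark about development are never joined. The rule is met at 2/15, an observed rate of 13.3%. The remark speaks of 20%, which as an observed rate would need 3/15. Section 8.1 writes of a true response rate for the null and again for the power, but the development sentence drops the word "true". Read by itself, it could mean the rate to be seen in the data.

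If both readings were live, a cohort with exactly 2/15 could be reported either as a success (null rejected) or as short of what was called clinically meaningful. The choice could then be made with the result in hand, in an open-label trial. The shared phrase in the Cohort 2 hypothesis seems to add to the doubt. The planned interval would not settle it either, because at 2/15 it covers both 3% and 20%.

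**Working it through.** **Inputs, all from Section 8.1.** Null rate 3%; design alternative 20%; stage 1 of 10 patients, stop at 0 responses; stage 2 of 5 more; reject at a total of 2 or more. Let X1 be binomial (10, p) and X2 binomial (5, p), independent.

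**Reproducing the plan's figures (2 or more of 15).**

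P(reject) = P(X1 ≥ 2) + P(X1 = 1) × P(X2 ≥ 1)

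- p = 3%: P(X1 = 0) = 0.97^10 = 0.7374; P(X1 = 1) = 10 × 0.03 × 0.97^9 = 0.2281; P(X1 ≥ 2) = 0.0345; P(X2 ≥ 1) = 1 − 0.97^5 = 0.1413. Result: 0.0345 + 0.2281 × 0.1413 = 0.0667, as stated.
- p = 20%: P(X1 = 0) = 0.1074; P(X1 = 1) = 0.2684; P(X1 ≥ 2) = 0.6242; P(X2 ≥ 1) = 1 − 0.8^5 = 0.6723. Result: 0.6242 + 0.2684 × 0.6723 = 0.8047, which agrees with the stated 80%.

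**The other reading: an observed 20%, or 3 or more of 15, with the same stage 1 stop.**

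P(3 or more) = P(X1 ≥ 3) + P(X1 = 2) × P(X2 ≥ 1) + P(X1 = 1) × P(X2 ≥ 2)

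- p = 20%: 0.3222 + 0.3020 × 0.6723 + 0.2684 × 0.2627 = 0.5958.
- p = 3%: 0.0028 + 0.0317 × 0.1413 + 0.2281 × 0.0085 = 0.0092.

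Neither figure appears in the plan. Its 80% belongs to the count rule alone.

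**Where the readings differ.** They agree on 0/10 and 1/15 (no) and on 3/15 or more (yes). They differ only at exactly 2/15:

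| True rate | 2 or more | 3 or more | Exactly 2 (difference) |
|---|---|---|---|
| 3% | 6.7% | 0.9% | 5.8% |
| 10% (assumed, for illustration) | 42.3% | 18.1% | 24.1% |
| 20% | 80.5% | 59.6% | 20.9% |

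If the two cohorts are independent with the same true rate (an assumption), the chance that at least one ends at exactly 2/15 is 1 − (1 − 0.2089)² = 37.4% at 20%, and 1 − (1 − 0.0575)² = 11.2% at 3%.

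**The interval at 2/15.** Taking exact binomial to mean Clopper-Pearson, the 90% interval is 2.4% to 36.3%. It includes 3% although the test rejects, because it allows 5% in each tail, while the chance of 2 or more of 15 at 3% (ignoring the early stop) is 7.3%. The mismatch comes from two different error levels. The plan gives the interval no part in the decision.

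**The case for a change.** The best argument for a change is that the plan attaches the words about proceeding to the 20% rate and not to rejection, and that no other section supplies the link. Section 3.1 gives no number, Section 5.11 deals with early termination, and Section 8.2 gives only the sample size. The affected result is not rare. It is the lowest rejecting count, and at a true 3% it makes up 0.0575 / 0.0667 = 86% of all rejections. One sentence would close the gap.

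The missing link is real, and so are the probabilities. They are, however, chances of landing on 2/15, not chances of a wrong conclusion. The 86% follows from a small design with a low null rate; it is already inside the stated type I error. The shift of 20.9 points matters only if one adopts a reading that contradicts the plan's own power. No sentence asks for an observed 20% or for 3 of 15.

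The Cohort 2 wording does not help the objection. Section 3.1 speaks of responses, not of a rate, and Section 8.1 gives both cohorts the same test, so there is no separate Cohort 2 criterion to reconcile. Nor is the development remark a binding algorithm: Section 5.11 shows that the drug's future also depends on its developers' plans and on supply.

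**Conclusion.** No change follows. At 2/15 the plan gives one primary result: the 3% null is rejected, at the stated error rate. That cannot be altered after the data are seen. The sentence on 20% comes directly after the statement of power at a true rate of 20%, and it is naturally read as the reason for choosing that alternative. The figures support this: 80.5% power under the count rule matches the plan, while 59.6% under an observed-20% rule does not.

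What is left is an unwritten convention that analysts of a two-stage design would supply: the alternative is a true rate, and rejection is the signal in favour of going on. Writing it down would alter no test, error rate, sample size or stopping rule. Moving to 3 of 15 would be a different trade-off, not a correction: a type I error of 0.9% instead of 6.7%, at the price of 20.9 points of power at a true 20%. A report of a 2/15 cohort should simply give the rejection, the observed 13.3% and the wide interval side by side.

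This rests on reading 20% as the design alternative and on Clopper-Pearson for the interval. The per-cohort probabilities are exact for the design as stated.
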